#### Withdrawal during treatment period:

Subjects who discontinue between Day 1 and Month 3 should undergo the procedures required at Month 6 (except the DXA scan and the endometrial biopsy if a biopsy was obtained at screening) and will not enter the 6-month follow-up period.

Subjects discontinuing the study treatment between Month 3 and Month 6 should undergo the procedures required at Month 6. These subjects will enter a 6-month follow-up period and will continue daily eDiary recording for 6 months and up to Month 6 FU visit in order to continue to collect efficacy data.

PK sampling is not required if the subject had no IMP administration the day prior to the withdrawal visit.

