#### Withdrawal during follow-up period:

Subjects discontinuing participation in the study during the follow-up period should undergo the procedures required at Month 6 FU visit, which includes completion of all ClinRO and ePRO questionnaires, except the DXA in case of discontinuation before Month 3 FU visit.

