** At the end of the 6-month follow-up, subjects with a BMD decrease from baseline of > 1.5% for lumbar spine and > 2.5% for total hip will have an additional DXA scan 6 months later.

Figure 1: Study design

All subjects received once daily either linzagolix 75 mg alone (with ABT placebo) or linzagolix 200 mg combined with low dose ABT, or placebo (linzagolix placebo with ABT placebo) for 6 months. ABT was a combination of estradiol (E2) 1 mg and norethisterone acetate (NETA) 0.5 mg. Linzagolix or its corresponding placebo was supplied as tablets for oral administration. ABT or its corresponding placebo was supplied as capsules for oral administration.

Linzagolix/placebo treatments were provided in monthly treatment kits, packaged, labelled and administered in the same manner to protect the blinded nature of the trial.

ABT/placebo treatments were supplied as 3-monthly kits, packaged, labelled and administered in the same manner to protect the blinded nature of the trial.

Blinded treatment kit numbers corresponding to each subject's randomized treatment were provided through an IWRS.

Sponsor:	ObsEva		
Protocol:	18-OBE2109-002		
Document Version No.:	1.0	Document Date:	18-MAY-2021

The main analysis was planned to be performed after 6 months of treatment on all of the subjects' data up to Month 6. However, due to the early termination of the study, one summary and report of the data will be performed and will be focused on the safety results from all subjects regardless of treatment duration.

2.2. **Randomization Methodology**

Randomization was performed via a centralized IWRS. Subjects were randomized on Day 1 to one of three treatment groups in a 1:1:1 ratio for linzagolix 75 mg, linzagolix 200 mg with ABT and placebo.

Subjects were randomized into permuted blocks of a pre-determined length.

There was no stratification.

2.3. **Stopping Rules and Unblinding**

2.3.1. **Stopping Rules**

Subjects were informed that they had the right to withdraw from the study at any time, without prejudice to their medical care, and that they were not obliged to state the reason(s). Any withdrawal must be fully documented in the eCRF exit form.

The Investigator may have withdrawn a subject at any time if this was considered to be in the subject's best interest.

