The efficacy variables planned in the protocol will not be analyzed due to the early study termination and the low number of subjects randomized.

2.5.2. **Pharmacokinetic Variables**

The pharmacokinetic variables planned in the protocol will not be analyzed due to the early study termination and the low number of subjects randomized.

2.5.3. **Safety Variables**

Safety endpoints include:

- Change from baseline to each scheduled assessment in BMD measured by DXA of lumbar spine (L1-L4), femoral neck, and total hip
- Incidence and severity of treatment emergent adverse events (TEAEs)
- Incidence and severity of hypoestrogenic TEAEs (hot flush)
- Time to the first post-treatment menses
- Changes in clinical laboratory assessments (hematology, biochemistry, coagulation parameters, hormones, lipids and urinalysis) from baseline to each scheduled assessment
- Any pathological changes from baseline in the endometrium as assessed by histology from endometrial biopsies
- Changes from baseline to each scheduled assessment in any other safety parameter including weight, vital signs, ECG, gynecological assessments and endometrial thickness

Safety analyses are described in Section 4.8.

Note that the endpoint “Time to the first post-treatment menses” was initially planned in the protocol, but will not be described in this SAP, because the study was stopped prematurely, and all subjects couldn’t be followed to evaluate this endpoint.

2.5.4. **Exploratory Variables**

The exploratory variables planned in the protocol will not be analyzed due to the early study termination and the low number of subjects randomized.

Sponsor:	ObsEva		
Protocol:	18-OBE2109-002		
Document Version No.:	1.0	Document Date:	18-MAY-2021

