4.2.8.3. Partial and Missing Dates of diagnosis

For partial date of first medical diagnosis/treatment, first surgical diagnosis and most recent surgical diagnosis the following rules of imputation will be applied:

- If only Day is missing, Day will be imputed to 01.
- If Day and Month are missing:
 - o if Year is the same as the screening date, Date will be imputed to Screening Date.
 - o Otherwise, Day will be imputed to 01 and Month will be imputed to 07.
- If Date is completely missing, no imputation will be done.

Sponsor:	ObsEva		
Protocol:	18-OBE2109-002		
Document Version No.:	1.0	Document Date:	18-MAY-2021

4.2.9. **TVUS data**

If the depth recorded for a TVUS of uterus is 0 mm, the depth and the volume should be considered as missing (i.e., the assessment was done in 2 dimensions instead of 3 dimensions).

4.2.10. **Visit Windows**

For all analyses except for the DXA assessments and the diary questionnaires, the visits as collected in the eCRF will be used.

All visit dates are calculated from the date the patient started treatment in the main study (Day 1 visit of 18-OBE2109-002 Edelweiss 2).

DXA data

Visit windows rules for DXA assessments will be the following:

- The baseline DXA assessment will be derived as the latest non-missing DXA assessment with acceptable quality (accepted="Yes") prior to the Baseline visit or the first non-missing assessment with acceptable quality (accepted="Yes") done up to 10 days after the baseline visit if there is no assessment prior to baseline.
- The DXA assessment at Month 6 will be derived as the first non-missing DXA assessment with acceptable quality (accepted="Yes") and dated between Month 6 theoretical date (=Day 169) -28 days and Month 6 theoretical date + 28 days.
- The DXA assessment at Month 6 Follow-Up will be derived in the same way as the DXA assessment at Month 6. Theoretical date of Month 6 Follow-up is 168 days after Month 6 theoretical date or after treatment discontinuation.

Other safety data:

The endometrial biopsy screening window will include any assessment done prior to the first IMP dose.

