For other safety results, data from early discontinuation should be compared to theoretical visits dates. Only assessments within the window of theoretical date +/-14 days will be used for analyses, if it is planned to have a such assessment at this visit and no other assessment is in the window. If a subject discontinued in the main treatment period, date will be compared to the theoretical visit dates in main treatment period as described in Table 3. If a subject discontinued in the follow-up period, date will be compared to the theoretical visit dates in Follow-up period from

Sponsor:	ObsEva		
Protocol:	18-OBE2109-002		
Document Version No.:	1.0	Document Date:	18-MAY-2021

Table 4.

For unscheduled safety assessments, if the assessment occurs in a window of +/- 14 days of a planned eCRF visit for which it was planned per protocol to have such assessment, and no assessment was done for that visit, the assessment will be assigned to that visit. If the assessment is equally distant from two eCRF visits with no corresponding safety assessment, the assessment will be assigned to the next visit.

For biopsy, DXA assessment or laboratory assessment, if an assessment has been assigned in external data to a follow-up visit of the main study for subjects entered extension study, the visit of assessment should be reassigned with the same rules described above for unscheduled safety assessment.

Table 3 Theoretical Visit Dates in Main Treatment Period

Visit	Theoretical Date
Month 1	Day 29
Month 2	Day 57
Month 3	Day 85
Month 4	Day 113
Month 5	Day 141
Month 6	Day 169

Sponsor:	ObsEva		
Protocol:	18-OBE2109-002		
Document Version No.:	1.0	Document Date:	18-MAY-2021

Table 4 Theoretical Visit Dates in Follow-up

Visit	Theoretical Date
Month 1 FU	Month 6 date or treatment discontinuation date + 28
Month 2 FU	Month 6 date or treatment discontinuation date + 56
Month 3 FU	Month 6 date or treatment discontinuation date + 84
Month 4 FU	Month 6 date or treatment discontinuation date + 112
Month 5 FU	Month 6 date or treatment discontinuation date + 140
Month 6 FU	Month 6 date or treatment discontinuation date + 168

4.2.11. **Baseline Definition**

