The number of events will be also displayed for summary of AEs, for analysis of TEAE, serious TEAE non-serious TEAE and for post-treatment AE, by SOC and PT.

No formal hypothesis-testing analysis of adverse events incidence rates will be performed.

All adverse events occurring on study will be listed in subject data listings.

By-subject listings also will be provided for the following: Treatment Emergent Adverse event, serious Treatment Emergent adverse events; Treatment Emergent adverse events leading to permanent discontinuation of IMP and leading to permanent discontinuation of IMP leading to death; post-treatment adverse event.

Sponsor:	ObsEva		
Protocol:	18-OBE2109-002		
Document Version No.:	1.0	Document Date:	18-MAY-2021

4.8.3. **Bone Mineral Density (BMD) by DXA**

BMD of femoral neck, total hip and lumbar spine will be assessed by DXA at Baseline, Month 6 and Month 6 follow-up. Unacceptable DXA assessments (accepted="No") will not be summarized (hip, spine and femur considered separately).

In case of repeated values due to BMD loss $\geq 5\%$, the initial scan will be used in summaries. Initial and repeated scan values will be reported in the listings.

Calibrated values will be used if available, otherwise initial values will be considered.

BMD, expressed as both absolute values and Z-scores will be summarized at each visit in terms of actual values, changes from baseline for each anatomic location. For absolute values only, percent change from baseline and 95% confidence interval for the mean percent change from baseline within each group will be produced at each time point.

Percent change from baseline to Month 6 and Month 6 follow-up will be described and will also be summarized in categories of percentage with the following classes:

- No change or increase,
- Decrease $\leq 3\%$,
- Decrease $> 3\% \text{ and } \leq 5\%$,
- Decrease $> 5\% \text{ and } \leq 7\%$,
- Decrease $> 7\% \text{ and } \leq 8\%$,
- Decrease $> 8\%$.

All data will be listed.

4.8.4. **Laboratory Data**

Clinical laboratory values will be expressed using conventional SI units.

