Hematology, coagulation parameters, chemistry and lipids were assessed at screening and at each visit during the treatment period, as well as at the M1 FU and M3 FU visits. E2, progesterone (P4) and LH are assessed at each visit during the treatment period (not at screening visit), as well as at the M1 FU and M3 FU visits. Serum levels of the anti-Müllerian hormone (AMH) and fasting glucose were assessed on Day 1 only. Serum levels of the sex hormone-binding globulin (SHBG) were assessed on Day 1 and Month 3 and Month 6 visits.

Blood samples were to be analyzed by the central laboratory.

For hematology, coagulation parameters, chemistry and lipids, the actual value and change from baseline will be summarized for each visit for each treatment group. In the event of repeated values, the last non-missing value per study day/time will be used.

Evaluation of shifts for changes from baseline to all visits, and to last on-treatment value (including unscheduled assessments) according to the normal ranges with categories "Low", "Normal", "High"

Sponsor:	ObsEva		
Protocol:	18-OBE2109-002		
Document Version No.:	1.0	Document Date:	18-MAY-2021

and according to normal/abnormal/abnormal clinically significant information collected otherwise, will be provided. Note that a value will be considered as “on-treatment” if the collection is performed between the first and last intake administration (included).

For Liver Function Test (LFT) parameters (ALT, AST, ALP, total bilirubin, direct bilirubin, indirect bilirubin, GGT, albumin, LDH and Creatine Kinase), evaluation of shifts for changes from baseline will be extended by the worst (highest) on-treatment value (including unscheduled assessments) according to the normal ranges with categories “Low”, “Normal”, “High” will be provided.

For the lipid panel (Triglycerides, HDL, LDL, Total Cholesterol, LDL/HDL ratio), the percent change from baseline to each on-study visit will also be summarized.

For serum levels of P4, SHBG and LH, only the actual values at each time point will be summarized. Note: in the event of repeated values, the last non-missing value per study day/time will be used.

In addition, for E2, the proportion of subjects with the following categories:

- E2 <20 pg/mL,
- E2 between ≥20 and <60 pg/mL,
- E2 ≥60 pg/mL

at each visit and for each treatment group will be provided in tables.

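### The Month 6 DXA window in SAP 4.2.10 is not tied to the last dose: an exit scan about three months off drug can be tabulated as Month 6, while the required withdrawal scan gets no row

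*SAP*

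**What the plan says.** - **DXA windows (SAP 4.2.10).** The Month 6 DXA is the first non-missing, accepted scan "dated between Month 6 theoretical date (=Day 169) -28 days and Month 6 theoretical date + 28 days". The Month 6 FU scan is derived in the same way, around a date 168 days after Month 6 or after treatment discontinuation. Neither rule refers to the last dose or to the study period in which the scan was taken.
- **BMD rows (SAP 4.8.3).** BMD "will be assessed by DXA at Baseline, Month 6 and Month 6 follow-up". No other time point is tabulated.
- **Other safety data (SAP 4.2.10).** The default is the visit as collected in the eCRF. An early-discontinuation result is used only within 14 days of a scheduled visit, and then only "if it is planned to have a such assessment at this visit and no other assessment is in the window".
- **Withdrawal from treatment (Protocol 10.7.2).** "Subjects discontinuing the study treatment between Month 3 and Month 6 should undergo the procedures required at Month 6". By Protocol 10.2.2.5 these include DXA, and a biopsy unless the endometrium is 5 mm or thinner.
- **Withdrawal from follow-up (Protocol 10.7.2).** The Month 6 FU procedures are due, "except the DXA in case of discontinuation before Month 3 FU visit". An exit at or after Month 3 FU therefore calls for a DXA.
- **Purpose (SAP 2.1).** The single report is to be "focused on the safety results from all subjects regardless of treatment duration".

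**The concern.** BMD is a named safety endpoint, and a reader will take the Month 6 row as bone density after about six months of treatment or close to its end. A window defined only by calendar date cannot tell a scan near the last dose from one taken months later in follow-up. For some early stoppers the rule passes over the scan taken near the end of treatment and uses an off-drug one. The value is then mislabelled, not merely missing.

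The second issue is one of coverage. The protocol asks women who stop between Month 3 and Month 6 for a DXA and, where indicated, a biopsy. The SAP gives many of these results no treatment-period row, although its stated focus is all subjects whatever their treatment duration. Shortened follow-up is documented: SAP 2.5.3 drops time to first post-treatment menses "because the study was stopped prematurely, and all subjects" could not be followed for it.

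**Working it through.** **Visit days.** With 28-day months, Month k falls on Day 1 + 28k. Month 3 = 1 + 84 = Day 85, Month 6 = 1 + 168 = Day 169 and Month 6 FU = 1 + 336 = Day 337. All match Protocol 10.2.

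**Windows.**
- Month 6 DXA: 169 − 28 = Day 141 to 169 + 28 = Day 197 (57 days).
- Month 6 FU DXA after a stop on Day s: s + 168 ± 28, so s + 140 to s + 196.
- Biopsy: Month 6 is the only treatment-period visit with a planned biopsy (Protocol Appendix A). 169 ± 14 gives Day 155 to 183.

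**Off-drug scan labelled Month 6.** Let s be the stop day and e the days from stop to exit scan. A stop after Month 3 means s ≥ 86. An exit DXA is due from Month 3 FU, so e ≥ 84. The scan counts as Month 6 if s + e ≤ 197 and no accepted scan falls earlier in Day 141 to 197.
- Largest s: 197 − 84 = 113. Largest e: 197 − 86 = 111. Earliest scan: 86 + 84 = Day 170.
- The Month 6 FU window opens at e = 140, so a scan at e ≤ 111 is never in it.
- The withdrawal scan does not pre-empt the exit scan if it is dated by Day 140. That allows a lag after stopping of up to 140 − 86 = 54 days for a stop on Day 86, and 140 − 113 = 27 days for a stop on Day 113.

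| Visit timing | Stop day | Days off drug | Scan day |
|---|---|---|---|
| Nominal | 86–113 | 84–111 | 170–197 |
| Month 3 FU 7 days early (e ≥ 77) | 86–120 | 77–111 | 163–197 |
| Also Month 3 held 3 days early, stop from Day 82 | 82–120 | 77–115 | 159–197 |

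**Withdrawal DXA with no row.** A scan dated Day 86 to 140 is before the Month 6 window and far short of s + 140. If scans are done on the stop day, that is 140 − 86 + 1 = 55 of the 83 possible stop days (86 to 168). If the scan lags by 7 or 13 days, the affected stop days are 86–133 or 86–127; the unplaced scan dates still end at Day 140. The rule for unscheduled assessments does not help, because it too needs a planned visit within 14 days.

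**Withdrawal biopsy.** Dates from Day 86 to 154 (154 − 86 + 1 = 69 days) lie outside Day 155 to 183.

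All of these are calendar days, not shares of subjects.

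**The case against.** **The Month 6 row is what the protocol planned.** Protocol 13.5.5 summarises BMD at baseline and Month 6, and never promised an end-of-treatment row. Keeping a Day 90 scan out of a row labelled Month 6 is sound. This stands. The missing row is a gap in coverage, not a departure from the protocol.

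**The all-subjects statement is being stretched.** In SAP 2.1 it contrasts one report with the analysis once planned after six months. It does not promise every subject a value in every table, and the exposure and AE tables do cover all dosed subjects. This is partly right. It weakens the coverage argument but does not touch the mislabelled scan.

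**The off-drug path needs several things to coincide.** It needs an early stop, an early enough withdrawal scan (or none accepted), about three months in follow-up, exit by Day 197 and an accepted scan. This stands. A reader might infer from the early termination that such scans are common. The documents give no stopping or exit dates, and the SAP 2.5.3 remark concerns menses, not DXA timing.

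**The biopsy gap is less certain.** The eCRF-visit default in SAP 4.2.10 would close it if the withdrawal visit is labelled Month 6, and the eCRF is not available. Follow-up rows may also capture the subject: Protocol 10.2.3.1, 10.2.3.2 and Appendix B, read literally, call for a follow-up biopsy when none was done at Month 6. Protocol 10.4.5 can instead be read as needing no repeat after a benign withdrawal biopsy. A reader might infer that every withdrawal biopsy before Day 155 is lost. That goes too far. Before Month 3 a biopsy is asked for only where none was obtained at screening (10.7.2), and 10.4.5 waives it under three months of treatment. Only Day 86 to 154 is firm.

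**All data are listed, and the tables are descriptive.** True, but a listing does not correct a mislabelled value in a summary row that carries a 95% confidence interval.

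**Conclusion.** The concern holds in a limited form. As written, SAP 4.2.10 can place a scan taken 84 to 111 days off drug (about 77 to 115 with visit tolerances) in the Month 6 BMD row. It also leaves a required withdrawal DXA dated Day 86 to 140 in no row. A withdrawal biopsy on Day 86 to 154 has no treatment-period row unless the eCRF labels the visit Month 6.

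This rests on reading the DXA rule as written, by date alone, and on the withdrawal scan, if accepted, being dated before Day 141.

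The documents do not show how many subjects are affected. Nor do they show that the Month 6 row as a whole is unsound, or in which direction it would move: off-drug recovery of BMD is not quantified. Discontinuers scanned from Day 141 are already included. Severity is minor to should-fix.

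**What to change.** 1. **Date condition.** In SAP 4.2.10, require the Month 6 DXA to fall within a pre-stated interval of the last main-study dose, by the same rule in all arms, so that follow-up exit scans are not labelled Month 6. The sponsor chooses the length and states it before unblinding. For extension entrants, flag scans taken after the first extension dose in all arms. Excluding them only for placebo subjects who switch to active drug would make missingness differ by arm.
2. **End-of-treatment row.** Add it to the BMD and biopsy tables beside Month 6, not in its place. Use the last accepted post-baseline assessment within the same interval of last dose, and show treatment duration with it.

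**Cost.** One derived time point and one date condition, with no new data. The new row mixes exposure lengths, which is why duration must be shown. A few late scans leave the Month 6 row. Take 28 days as an illustration (not a figure set for this purpose in the documents) and dosing up to the day before the Month 6 visit (Protocol 11.2):

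| Month 6 visit | Last dose | Last eligible scan (+28) | Window days lost of 57 |
|---|---|---|---|
| Day 166 | Day 165 | Day 193 | 197 − 193 = 4 |
| Day 169 | Day 168 | Day 196 | 197 − 196 = 1 |
| Day 172 | Day 171 | Day 199 | 0 |

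A discontinuer scanned later than the chosen limit would lose her Month 6 value, which is the intended effect.

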4.2.12. Last treatment administration date, End of Study date and Period definitions

The last treatment administration date will be defined as the date of treatment termination recorded in the main period eCRF page. If this date is missing, the last date with a drug intake in eDiary prior to the Month 6 date or, for subjects who discontinued, the last date with available drug intake information in the subject eDiary will be used.

The end of study date will be the last assessment date in the main study defined as last eCRF or ediary date prior to and not including Month 6 for subjects who entered the Extension, and the last eCRF or ediary date in the main study or main follow-up if not. This will not necessarily be the same date as last assessment date as recorded in the eCRF.

Note: For summaries by visit (efficacy or safety), the Month 6 assessments will be included in the main study analyses. For Adverse Events, Concomitant Medications and Daily diaries, data collected on Month 6 date will be part of the extension for subjects entering the extension study and be part of the Follow-up period for subjects entering the main study follow-up period.

The main treatment period will be defined as Day 1 up to (Month 6 date -1) or the treatment discontinuation date.

The main follow-up period will be defined as the Month 6 date or (treatment discontinuation date+1) up to the end of study date (for subjects who entered into the main follow-up period).

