4.8.1. Extent of treatment exposure and compliance

4.8.1.1. Extent of treatment exposure

Duration of treatment (weeks) will be summarized for each treatment group. Duration is defined as: [(date of last treatment administration as described in section 4.2.12) - (date of first administration as collected in eCRF) +1] / 7.

Time on study (weeks) will be summarized for each treatment group, defined as: [(end of study date as described in section 4.2.12) – (first dose date) +1]/7

Exposure data will be reported in listings.

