4.8.1.2. Compliance

Lingazolix/Placebo Grey blister (200 mg or matching placebo), Lingazolix/Placebo Pink blister (75 mg or matching placebo) and Add-back therapy compliance from the study treatment accountability page among the Day 1- End of main study treatment period will be summarized by treatment group.

If Lingazolix/Placebo and Add-back therapy compliances from accountability data are missing, compliance will be computed from daily diary data.

Compliance will be computed as the number of days with pink tablet/grey tablet/Add-back capsule taken *100 divided by the number of days in the period (Month 6 visit date/withdrawal date - Day 1). Data from “Today” will be used primarily. If data from today is missing, date from “Yesterday” will be considered. If the e-diary is not completed for a day (neither “Today” nor “Yesterday”), it will be assumed that no intake of drug was taken on that day.

Study treatment overdose and misuse will be reported in a listing.

Compliances will be reported in a listing.

Sponsor:	ObsEva		
Protocol:	18-OBE2109-002		
Document Version No.:	1.0	Document Date:	18-MAY-2021

4.8.2. **Adverse Events**

Adverse events will be coded using the Medical Dictionary for Regulatory Activities (MedDRA) and displayed in tables and listings using System/Organ/Class (SOC) and Preferred Term.

Analyses of adverse events will be performed for those events that are considered treatment emergent (TEAEs), where treatment emergent is defined as AEs with a start date on or after the first dose of study drug through 30 days after discontinuation of study drug or Month 6 visit date, or any event that was present at baseline but worsened in intensity or was subsequently considered drug-related by the investigator through the end of the study.

Adverse Event tables will be presented for the following periods: Day 1 to Month 6 (treatment period) and Month 6 to Month 6 FU (follow-up period) as defined in section 4.2.12.

Adverse events starting more than 30 days after end of treatment will be considered as post-treatment AE.

Note: if an adverse event started after or at Month 6 visit date and if the subject entered the extension period, this adverse event will not be displayed for the main study, but only for the extension study.

For each of these 2 study periods, an overall summary table will be prepared presenting, by treatment group and overall, the number and percentage of subjects with

- any AE,
- any TEAE,

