4.8.7. Prior and Concomitant Medications

Prior and Concomitant medications will be coded using the WHO Drug dictionary. Frequencies and percentages will be presented for each treatment group and overall by the first level anatomical main (ATC 1) group and preferred name.

Prior medications are those the subject used prior to the first day of treatment.

All medications administered between the date of the first dose of study drug and the date of the last dose of study drug, inclusive, (i.e., all medications starting or ongoing during the time interval) are concomitant. A medication taken prior to Study Day 1 and continuing post Study Day 1 will be considered both prior and concomitant.

Concomitant medications tables will be presented for the following periods: Day 1 to Month 6 (treatment period) and Month 6 to Month 6 FU (follow-up period) as defined in section 4.2.12.

The use of prior and concomitant medications will be included in a by-subject data listing.

Prior interventional surgeries/procedures for endometriosis/endometriosis symptoms will also be summarized.

The use of Prior interventional surgeries/procedures for endometriosis/endometriosis symptoms will be included in a by-subject data listing.

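### When the eCRF termination date is missing, the SAP's fallback last-dose date for early stoppers does not require that drug was taken, so their treatment duration can be overstated

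*SAP*

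**What the plan says.** SAP 4.2.12 sets a primary rule: "The last treatment administration date will be defined as the date of treatment termination recorded in the main period eCRF page". Only if that date is missing does the diary come in, and one sentence then gives two fallbacks.

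- Subjects who did not discontinue: "the last date with a drug intake in eDiary prior to the Month 6 date".
- Subjects who discontinued: "for subjects who discontinued, the last date with available drug intake information in the subject eDiary will be used".

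The first needs an intake and stops before Month 6. The second needs only that intake information is available, and it has no upper limit.

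The date is used explicitly in SAP 4.8.1.1, where treatment duration runs to the "date of last treatment administration as described in section 4.2.12". Other sections set windows with similar terms but do not cite 4.2.12:

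- SAP 4.8.4 counts a laboratory value as on-treatment if it falls between first and last intake.
- SAP 4.8.7 defines concomitant use as "All medications administered between the date of the first dose of study drug and the date of the last dose of study drug".
- SAP 4.8.2 defines treatment-emergent events as "AEs with a start date on or after the first dose of study drug through 30 days after discontinuation of study drug".

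**The concern.** During treatment the diary asks about intake every day (Protocol 10.2.2 and 11.7), so a woman who has stopped can go on recording that she took nothing. Under the discontinuer wording, her last such answer becomes her last administration date.

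This is out of step with the rest of the SAP. The actual-treatment derivation in 3.1 counts days on which tablets and capsule were taken, treats unanswered days as no intake, and uses nothing after discontinuation. The diary-based compliance rule in 4.8.1.2 also counts days taken. Only 4.2.12 would let a day without drug stand as the last dose.

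Such days are foreseeable. Protocol 10.7.2 allows for a withdrawal visit with no drug on the preceding day and tells early stoppers to complete diary questionnaires after stopping. The serum calcium rule in Protocol 10.7.2.1 provides for interruption, a repeat test within 2 weeks, and then possible permanent discontinuation.

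After early termination the report rests on safety, and treatment duration is one of its main descriptors.

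**Working it through.** The plan states no figure that depends on this rule, so there is none to reproduce. The check applies the SAP's own duration formula under both fallbacks.

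**Inputs**

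- Duration in weeks = (last date − first date + 1)/7, from SAP 4.8.1.1. The first date is Day 1.
- L = last diary day with drug reported as taken.
- g = days from L to the last intake answer of any kind. The documents give no value; 3, 7, 14 and 28 are assumptions.

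**Direction.** The last day with any intake answer cannot come before the last day with a positive one, so g ≥ 0. Against diary-recorded intake, the literal rule is either correct or too long, never too short.

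**Size.** Requiring an intake gives L/7. The literal wording gives (L + g)/7. The difference is g/7 weeks, and the relative excess is g/L.

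Two women who stop before Month 3 (Day 85), with last intake on Day 29 or Day 57:

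| g (days) | Excess (weeks) | L = 29: 29/7 = 4.14 weeks becomes | L = 57: 57/7 = 8.14 weeks becomes |
|---|---|---|---|
| 3 | 0.43 | 32/7 = 4.57 (+10%) | 60/7 = 8.57 (+5%) |
| 7 | 1.00 | 36/7 = 5.14 (+24%) | 64/7 = 9.14 (+12%) |
| 14 | 2.00 | 43/7 = 6.14 (+48%) | 71/7 = 10.14 (+25%) |
| 28 | 4.00 | 57/7 = 8.14 (+97%) | 85/7 = 12.14 (+49%) |

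With g = 0 nothing changes. In an arm of n subjects, the mean duration rises by the sum of g over affected subjects, divided by 7n. Neither n nor the number affected is given.

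**Do the cleaning rules remove these answers?** SAP Appendix A, case 4 in Tables 5 and 6, deletes intake answers when a subject entered main follow-up but her diary stayed in treatment mode. The cut-off is the Month 6 visit date.

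- Women who stop before Month 3 do not enter follow-up (Protocol 10.7.2), so no deletion rule covers them.
- For women who stop between Month 3 and Month 6 the rule may apply, but its cut-off is unclear.
- No rule addresses no-intake days between the last dose and the withdrawal visit.

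**The case against.** **The fallback may never be used.** The eCRF date governs. Protocol 10.7.2 requires every withdrawal to be fully documented in the eCRF exit form, and Protocol 14.3 delays database lock until data clarifications are resolved. This stands. A reader might infer that early stoppers as a group have inflated exposure, but a discontinuer with a recorded date is unaffected.

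**The wording may only be loose.** Under a heading about last treatment administration, intake information could mean a recorded intake. That is possible, and the SAP never says that no-intake answers count. But the same sentence uses a different and stricter phrase for the other subjects, and a programmer following the text would apply the difference.

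**Extreme examples do not hold.** A reader might picture a woman who stops at Day 100 and whose diary stays in treatment mode to Day 168: 168/7 = 24.0 weeks against 100/7 = 14.3, or +68%. She stopped after Month 3, so she enters follow-up, where the diary as designed has no intake item (Protocol 10.2.3). If her diary was left in treatment mode, Appendix A case 4 may delete those answers. The documents do not support this as an expected result.

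**The downstream effects are mostly not stated.** A reader might infer that off-drug laboratory values become on-treatment values and that the 30-day adverse-event window moves later. The laboratory and concomitant-medication sections speak of last intake or last dose without citing 4.2.12; a programmer would probably use the same derived date, but that is inference. The adverse-event window runs from discontinuation of study drug, which 4.2.12 does not equate with last administration, so no shift there is established. Diary-based compliance uses the Month 6 or withdrawal date and is not affected. Adverse-event tables are simple subject incidence, and no exposure-adjusted rates are planned.

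**Conclusion.** A real but narrow defect. Followed as written, the discontinuer fallback can record a day without drug as the last administration date, and against diary-recorded intake the error goes only towards longer exposure. The one explicit consequence is the treatment-duration summary, overstated by g/7 weeks per affected subject: 0.4 to 4.0 weeks for an assumed g of 3 to 28 days.

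An effect requires three things together: a subject who discontinued, a missing eCRF termination date, and trailing answers that no drug was taken. The documents do not say how many subjects meet all three; it may be few or none. The clearest exposure is among women who stopped before Month 3, and in the days between last dose and withdrawal visit. The laboratory and concomitant-medication windows probably follow the same date. An effect on treatment-emergent classification is not shown.

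**What to change.** In SAP 4.2.12, replace the discontinuer fallback with the last diary date on which drug was reported as taken, using the Today entry or, if that is missing, the Yesterday entry of the following day. This matches the intake requirement for the other subjects and the Today/Yesterday handling in 3.1 and 4.2.8.2. State whether the windows in 4.8.4 and 4.8.7 use this date, and say how the treatment discontinuation date used elsewhere relates to it. Add a listing of the subjects for whom the fallback was used, so that its reach is visible.

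The cost is one phrase, one line of derivation code and a short listing. The change does not depend on treatment allocation, so it can be settled before unblinding. There is a small downside: Appendix A describes diaries left in screening mode, with no intake answers although the woman was on treatment. If intake answers are absent while drug was taken, the diary-based date may fall before the true last dose. The listing would show such cases for individual review.
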